8.3.1. Primary Efficacy Analyses

The co-primary endpoints are OS and independently-assessed PFS. PFS will be determined by adjudicated disease progression (disease progression demonstrated by radiographic imaging or other appropriate modality), or death due to any cause, described in [Section 8.2.1](#). Subjects will be stratified at randomization by whether they had 2 or ≥ 3 prior HER2+ MBC regimens in the metastatic setting; whether they had visceral disease or non-visceral only; their tumor’s hormone receptor status, and their geographic region.

When 419 centrally assessed PFS events have occurred the primary PFS analysis will be performed. The median time to PFS and corresponding two-sided 95% confidence intervals will be calculated using the product limit estimator and displayed using a Kaplan-Meier graph, by treatment group. A log-rank test controlling for hormone receptor status, number of prior HER2-directed regimens in the metastatic setting, visceral disease status, and geographic region will be used to test the null hypothesis of no difference in the time to PFS between the two treatment groups at the alpha level of 0.01. A stratified Cox Proportional hazard model will be used to estimate the hazard ratio. PFS events will continue to be captured after the primary PFS analysis and a secondary, descriptive, analysis similar to the primary will be performed at the time of the primary OS analysis. When the PFS analysis is performed, an interim analysis will be performed on the OS endpoint. When 378 deaths have occurred, the primary (final) OS analysis will be performed. The median time to OS and corresponding two-sided 95% confidence intervals will be calculated using the product limit estimator and displayed using a Kaplan-Meier graph, by treatment group. A log-rank test controlling for hormone receptor status, number of prior HER2-directed regimens in the metastatic setting, visceral disease status, and geographic region strata will be used to test the null hypothesis of no difference in the survival between the two treatment groups as described in the overview of [Section 8.3](#).

The co-primary efficacy analyses will be performed on the intent to treat (ITT) population defined as all subjects randomized into the study. Sensitivity analyses will be performed to

investigate the impact of dropout between the two treatment groups on the treatment effect estimate.

8.3.1.1. Sensitivity Analyses

The following sensitivity analyses for PFS will be performed:

1. If there are more than 10% of patients that start a new anti-cancer therapy prior to the documentation of a PD, the initiation of the new therapy will be considered as an event and the start date for the new anti-cancer therapy will be considered the PFS event date.
2. Similar to the primary analysis, a sensitivity analysis will be done without stratifying by the randomization strata. Identical event and censoring rules will be used as described in the primary PFS analysis ([Section 8.2.1](#)).
3. A sensitivity analysis will be performed using all tumor assessments and deaths. This means that new anti-cancer therapy will not be used to exclude tumor assessments and deaths and tumor assessments will be used even if a subject misses 2 or more visits prior to progression being documented.
4. Similar to the primary analysis, a sensitivity analysis will be done using interval censoring estimation to address any potential imbalance in intermittent missing assessments.

For OS, an unadjusted analysis without stratifying by the randomization strata will be performed.

8.3.2. Secondary Efficacy Analyses

The secondary endpoints of ORR, CBR and duration of response will be assessed using the centrally reviewed tumor assessments as well as the investigator tumor assessments. The secondary endpoint of time to intervention for symptomatic CNS disease will only use the investigator-reported data.

The treatment difference in the secondary efficacy endpoint of investigator assessed PFS will be assessed with the product limit estimate of the median time to event. Differences between treatment groups will be examined using a log rank test statistic stratified by hormone receptor status, number of prior HER2-directed regimen in the metastatic setting, visceral disease status, and geographic region strata (similar to the analyses for the primary endpoints). All time-to-event endpoints including time to intervention for symptomatic CNS disease will be displayed using a Kaplan-Meier survival plot.

For the secondary endpoints of ORR and CBR the subjects included in the analyses are those that had measurable disease (per RECIST v1.1) at screening. Any tumor assessments after the start of new anti-cancer therapy will not be included in the analyses for these two endpoints. The treatment difference in the secondary efficacy endpoints of ORR and CBR will be analyzed using a Cochran-Mantel-Haenzel (CMH) Chi-square test, stratified on hormone receptor status, number of prior HER2-directed regimens in the metastatic setting, geographic region and disease category (visceral vs. non-visceral only).

Duration of response will be summarized by treatment group for the patients that responded. If there are patients that continue to respond, they will be censored at their last tumor assessment and a Kaplan-Meier analysis will be done to estimate the duration of response.

With the exception of the CNS endpoint, which will be tested only after the null hypothesis is rejected for OS; all other secondary endpoints are descriptive analyses and will be done at the time of the primary PFS analysis.

Cumulative incidence of time to intervention for symptomatic CNS is defined as time from randomization to the start of therapy for symptomatic CNS. Competing event are deaths prior to intervention for symptomatic CNS. Gray's test (Gray, 1988) stratified for factors used in the randomization will assess the equality of cumulative incidence functions between the treatment arms. Additionally, the Kaplan Meier method, stratified log-rank test, and Cox proportional hazard model will be performed without considering competing events.

As a sensitivity analysis to the secondary CNS endpoint, the time to progressive central nervous system (CNS) lesions will be analyzed using the centrally reviewed tumor assessments as well as the investigator tumor assessments. Time to progressive CNS lesions is defined as the time interval from the date of randomization until the first date on which a scheduled or unscheduled visit documents the appearance of newly diagnosed or progressive CNS lesions, per RECIST v1.1. If there is no evidence of CNS progression, the subject will be censored at the last assessable evaluation on study or prior to new anti-cancer therapy, if applicable. Competing events include progression at other sites and deaths prior to progressive CNS. Gray's test (Gray, 1988) stratified for factors used in the randomization will assess the equality of cumulative incidence functions between the treatment arms. Additionally, the Kaplan Meier method, stratified log-rank test, and Cox proportional hazard model will be performed without considering competing events.

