All safety endpoints will be summarized by treatment group and visit when appropriate. Adverse events and

serious adverse events will be coded using the Medical Dictionary for Regulatory Activities (MedDRA) coding system v.15 or later, and they will be tabulated by organ system and preferred term. All AEs will be graded according to the NCI CTCAE v.4.0. Differences in the incidence of the most common AEs and SAEs between the two treatment groups will be investigated using a CMH chi-square test, stratified on hormone receptor status, number of prior HER2-directed regimens in the metastatic setting, geographic region, and disease category (visceral vs. non-visceral only).

Interim Analysis:

No interim PFS or OS analysis for early stopping is planned. An interim analysis of OS will be conducted at the time of the final PFS analysis (at the alpha level of 0.002 at the interim analysis and 0.038 for the final analysis).

Final Analysis:

A final PFS analysis will be conducted when 419 PFS events have occurred.

[figure not shown]
A final OS analysis will be conducted when 378 deaths have occurred.

An analysis of all efficacy and safety endpoints will occur after the long-term follow-up phase has been completed.

Study Design Diagram / Schedule of Procedures:

A diagram of the study design is provided below in [Figure 1](#). A schedule of procedures is included in [Appendix 1](#).

Figure 1. Study Schema of PUMA-NER-1301

PFS: progression-free survival; OS: overall survival.

End of treatment is defined as documented disease progression, unacceptable toxicity or withdrawal of consent.

TABLE OF CONTENTS

1	LIST OF ABBREVIATIONS	16
2	INTRODUCTION.....	19
2.1	Background	19
2.1.1	General Therapeutic Area	19
2.2	Current Therapies	19
2.2.1	The Epidermal Growth Factor Receptor Family (ErbB Receptors)	19
2.2.2	Cancer Therapies Targeting HER Receptors	20
2.2.2.1	Trastuzumab	20
2.2.2.2	Pertuzumab [Perjeta™]	20
2.2.2.3	Pertuzumab in Combination with Trastuzumab	21
2.2.2.4	Ado-trastuzumab Emtansine (T-DMI[Kadcyla™])	21
2.2.2.5	Lapatinib	22
2.2.2.6	Lapatinib in Combination with Capecitabine	22
2.2.3	Neratinib	23
2.2.3.1	Preclinical Data	23
2.2.3.2	Neratinib Phase I and Pharmacokinetic Data	23
2.2.3.3	Neratinib Single-Agent Activity in Patients with HER2+ Breast Cancer	24
2.2.3.4	Neratinib in Combination with Capecitabine	25
2.3	Study Rationale	26
3	STUDY OBJECTIVES.....	27

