2.6. Sample Size Determination

The co-primary endpoints will be analyzed using an overall Type I error rate of 0.01 for PFS and 0.04 for OS. To detect a hazard ratio (experimental vs. control) of 0.70 with approximately 85% power, 419 PFS events (PD/Deaths) are required to be observed; this assumes a median (ITT) PFS of 8.0 months (34.7 weeks) for the experimental arm (neratinib plus capecitabine) and 5.6 months (24.3 weeks) for the control arm (lapatinib plus capecitabine).

It is expected that the 419th event will be observed at approximately 26 months after the first subject is enrolled, which would correspond to approximately half of the death events needed to be observed. At this time, an interim analysis on OS will also be performed. For the OS endpoint, a group sequential method will be employed to maintain the overall Type I error rate at 0.04. Specifically, Lan DeMets alpha spending function approximating the O’Brian-Fleming boundaries will be calculated to create appropriate critical values to which the log rank statistic will be compared (De Mets and Gordon Lan, 1994). If 50% of the deaths are observed at the interim OS analysis, the boundary using the Lan-DeMets alpha spending function is shown in Table 1 for OS interim analysis.

Table 1: Spending Function

Information Fraction	Expected Death Events	Study Month	Boundary (Reject H_0)	2-Sided Significance Level*
50%	185	26	3.066	0.002
100%	378	50	2.058	0.039

* This significance level relates to the 0.04 alpha allocation to OS but will be updated if the entire 0.05 can be allocated to OS.

These boundaries are designed to detect a hazard ratio (experimental vs. control) of 0.725 with approximately 85% power. Overall, 378 OS events (deaths) are required to be observed; this assumes a median (intent to treat [ITT]) OS of 30.3 months for the experimental arm (neratinib plus capecitabine) and 22.0 months for the control arm (lapatinib plus capecitabine).

Approximately 600 subjects will be enrolled and randomized equally between the two treatment arms. This sample size assumes a 1% drop out rate per 12 months (52 weeks) equally distributed between the treatment arms for the PFS endpoint.

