8.2.6. Clinical Benefit Rate (CBR)

[figure not shown]
Clinical benefit rate is the proportion of patients who achieve overall tumor response (confirmed CR or PR) or stable disease (SD) lasting for at least 24 weeks from randomization. Tumor assessments after the initiation of new anticancer therapy will not be included when determining CBR.

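### Clinical benefit rate needs 24 weeks of stable disease but is analysed at an event-driven PFS cutoff with no follow-up condition, so both arms' rates can be understated

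*SAP*

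**What the plan says.** - **Definition.** SAP 8.2.6 accepts a confirmed CR or PR, or "stable disease (SD) lasting for at least 24 weeks from randomization".
- **Denominator.** SAP 8.3.2: "For the secondary endpoints of ORR and CBR the subjects included in the analyses are those that had measurable disease (per RECIST v1.1) at screening". Protocol inclusion criterion 5 requires a measurable lesion, so this is close to all 600 patients. The supplemental SAP also lists an ITT table of ORR and CBR. Neither version has a follow-up condition.
- **Timing.** SAP 8.3.2, after setting the CNS endpoint apart: "all other secondary endpoints are descriptive analyses and will be done at the time of the primary PFS analysis". SAP 8.3.1 fixes that moment: "When 419 centrally assessed PFS events have occurred the primary PFS analysis will be performed". SAP 2.6 gives a forecast date: "It is expected that the 419th event will be observed at approximately 26 months after the first subject is enrolled".
- **Later looks.** SAP 8.3.1 states that "PFS events will continue to be captured after the primary PFS analysis" and plans a second, descriptive PFS analysis at the final OS analysis. It plans no such repeat for CBR. The protocol synopsis, under Final Analysis, says: "An analysis of all efficacy and safety endpoints will occur after the long-term follow-up phase has been completed".
- **Not stated.** Neither document gives the length or shape of accrual, a minimum follow-up for CBR, or a rule for patients in ongoing stable disease with less than 24 weeks.

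**The concern.** CBR is a proportion with a fixed time criterion, but it is computed at a calendar time set by PFS events. PFS and duration of response have censoring rules for patients with short follow-up. A proportion compared by a CMH test has no such mechanism. A patient randomized four months before the cutoff, in stable disease and still on treatment, has not met the definition and is still in the denominator.

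At stake are the reported rates. They would depend partly on how fast the last patients were recruited. They would also not be comparable with rates from studies in which every patient passed 24 weeks, such as the CBR that Protocol 2.2.3.4 cites for lapatinib plus capecitabine.

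**Working it through.** **1. Reproduce the plan's event count.** SAP 2.6: "To detect a hazard ratio (experimental vs. control) of 0.70 with approximately 85% power, 419 PFS events (PD/Deaths) are required to be observed". With two-sided alpha 0.01, Freedman's formula gives (2.576 + 1.036)² × (1.70/0.30)² = 419, an exact match.

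**2. Infer accrual, since it is not stated.** Inputs from SAP 2.6: 300 patients per arm, median PFS 8.0 and 5.6 months, 419 events at about month 26. Exponential PFS is assumed. For uniform accrual over A months, with λ = ln 2 / median,

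events per arm = 300 × [1 − (e^(−λ(26−A)) − e^(−26λ)) / (λA)].

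At A = 24.0 this gives 193.8 (neratinib) + 225.2 (lapatinib) = 419.0. With the SAP's 1% yearly dropout, A is 23.9.

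**3. Share with under 24 weeks at month 26.** 24 weeks = 5.52 months. Share = [24 − (26 − 5.52)] / 24 = 3.52/24 = 14.7%, or 88 of 600 (14.1% with dropout).

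**4. Vary the accrual shape.** Each row is solved for 419 PFS events at month 26 without dropout. Deaths use the stated OS medians of 30.3 and 22.0 months. The plan states 185 deaths at month 26 and 378 at month 50.

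| Cumulative accrual | Length (months) | Under 24 weeks | Deaths, month 26 | Deaths, month 50 |
|---|---|---|---|---|
| Uniform | 24.0 | 14.7% | 182 | 380 |
| ∝ t^1.25 | 22.5 | 11.3% | 177 | 378 |
| ∝ t^1.5 | 21.5 | 6.9% | 174 | 376 |
| ∝ t² | 20.0 | 0% | 171 | 374 |

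Solving uniform accrual from the death milestones instead gives 12.8% (185 deaths at month 26) and 16.7% (378 deaths at month 50).

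**5. From short follow-up to understated CBR (uniform accrual).** Patients who have already progressed or died without a response, or who have a confirmed response, are classified correctly. About 10.6% of the neratinib arm and 9.3% of the lapatinib arm have short follow-up and are still progression-free at the cutoff: 32 + 28 = 60 of the 88.

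- *Nobody responds.* PFS at 24 weeks is e^(−λ × 5.52) = 62.0% and 50.5%. The loss is 0.147 × 62.0 = 9.1 points and 0.147 × 50.5 = 7.4 points (8.8 and 7.1 with dropout). The difference falls from 11.5 to 11.5 × 0.853 = 9.8 points. The ratio between arms stays at 1.23.
- *Assumed confirmed response rates of 25% and 20%.* Protocol Table 1 gives 23.7% for the control regimen. A simulation stopped at the 419th event takes CBR from 67.4% to 60.6% (neratinib) and from 56.2% to 50.3% (lapatinib), losses of 6.8 and 5.9 points. Simple arithmetic on the stable-disease part gives 0.147 × (67.4 − 25) = 6.2 and 0.147 × (56.2 − 20) = 5.3. The remainder is consistent with responses not yet confirmed at the cutoff.
- *High response rate.* Protocol 2.2.3.4 cites ORR 44.2% and CBR 57.7% for lapatinib plus capecitabine, so 13.5% benefit through stable disease alone. If every eventual responder is already counted, the loss is 0.147 × 13.5 = 2.0 points.

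These losses scale with the share in step 4 and vanish if accrual ends at least 24 weeks before the cutoff.

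**The case against.** The strongest case on the other side has five parts.

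- *The 15% is not the plan's figure.* Correct. It is back-solved under uniform accrual and exponential PFS. Uniform accrual fits the month-26 deaths best, but the test is weak. The plan calls that milestone only approximately half of the deaths, and the t^1.25 curve fits month 50 at least as well. The range of 0 to about 17% must be given with it.
- *Short follow-up is not misclassification.* Also correct. A reader might infer that 15% of patients are scored wrongly. Step 5 shows that the effect on the rate is roughly half of that or less.
- *No passage says that these patients count as no benefit.* True. It follows from reading the definition and the denominator together. No other rule is written, however, and two programmers could handle these patients differently.
- *CBR is descriptive.* A reader might infer that the planned test loses power or that a trial conclusion is at risk. The documents do not support this. SAP 8.3 makes tests of secondary endpoints other than CNS descriptive, and CBR has no alpha and no planned power. Randomization balances short follow-up, so there is no bias toward either arm. Nor would the restricted early set, being smaller, recover much precision.
- *A mature analysis is already promised.* The protocol synopsis plans one for all efficacy endpoints after long-term follow-up, and the SAP supplements the protocol, so it would be wrong to say that none is planned. But the SAP places CBR at the PFS trigger, repeats only PFS later, and does not say which CBR is definitive.

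**Conclusion.** The point stands as a moderate defect in a descriptive endpoint. Followed literally, the SAP understates absolute CBR in both arms and shrinks the absolute difference, by an amount that depends on recruitment speed. Under uniform accrual of about 24 months, about 15% of patients lack 24 weeks at the cutoff. The understatement is then about 2 to 7 points per arm with plausible response rates, and about 7 to 9 points if nobody responds. Under rising accrual, 0 to 11% lack 24 weeks and the effect shrinks in proportion, possibly to nothing. These sizes assume exponential PFS at the planned medians and a cutoff at month 26. The relative comparison is little affected, and no confirmatory conclusion is touched.

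**What to change.** In SAP 8.3.2:

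1. Name as definitive the CBR in all patients with measurable disease at the final OS analysis, where updated PFS is already planned. This agrees with the protocol's later analysis of all endpoints.
2. At the primary PFS cutoff, report CBR also, or only, in patients randomized at least 24 weeks plus 17 days before the cutoff. The 17 days are the 14 days allowed from randomization to first dose (Protocol 4.2.2) plus the 3-day scan window. Select by randomization date alone, so that early progressors and early responders are treated alike.

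The cost is two sentences and one extra table. Under uniform accrual the early estimate uses about 15 to 17% fewer patients: 24 weeks plus 17 days is 6.08 months, so (24 − 19.92)/24 = 17.0% are left out and about 249 per arm remain. The early set also departs from the ITT population that SAP 4 names for secondary efficacy endpoints, so it should be labelled as a follow-up-restricted set.

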8.3.3. Other Efficacy Analyses

8.3.3.1. Health Outcome Assessments

The following health outcomes endpoints will be assessed at Cycle 1 Day 1 of the study (at any time within 24 hours of randomization) and at the end of every 6 weeks (\pm 3 days) starting from Cycle 1 Day1 as indicated in the Schedule of Procedures included in the protocol.

- European Organization for the Research and Treatment of Cancer Quality of Life Questionnaire C-30 (EORTC QLQ-C30), version 3
- EORTC QLQ Breast Cancer Module (BR23)
- The EuroQol (EQ-5D) multi-dimensional health status questionnaire

8.3.3.1.1. EORTC QLQ C30 and BR23

The EORTC QLQ-C30 is a questionnaire developed to assess the quality of life of cancer patients which includes measures of physical functioning [PF], role functioning [RF], emotional functioning [EF], social functioning [SF], global QoL, and fatigue [FA]). It is supplemented by the breast cancer module (BR-23) which includes measures of body image, sexual functioning, systemic therapy side effects, breast symptoms, and arm symptoms. The complete questionnaire includes 53 items; 23 of them are specific of breast cancer. Patients will be asked to indicate the extent to which they have experienced symptoms or problems using a 4 point scale as follows: 1, is not at all; 2, a little; 3, quite a bit and 4, very much. Patients are also asked to rate their overall

health and quality of life during the past week using a 7 point scale where 1 is very poor and 7 is excellent.

Patient responses on the level of severity on the EORTC QLQ C30 and BR23 dimensions will be used to derive the corresponding EORTC QLQ C30 and BR23 scores, as per published methodology.

8.3.3.1.2. EQ-5D-5L

The EuroQol questionnaire (EQ-5D-5L) is a brief, self-administered generic health status instrument consisting of two parts. In the first part respondents are asked to describe their current health state on 5 dimensions (mobility, self-care, usual activities, pain or discomfort, and anxiety or depression) with each dimension having 5 levels of function (1 = no problem, 2 = slight problem, 3 = moderate problem, 4 = severe problem, and 5= unable to function/extremely affected). The second part is a patient's self-rating of current health state on a Visual Analog Scale (EQ-VAS) with endpoints labeled 'best imaginable health state' and 'worst imaginable health state'. The EQ-5D-5L endpoints are the EQ-5D-5L Index which is derived by combining one level from each of the 5 dimensions and converting it to a single summary index or health utility value (Shaw et al., 2005) and the EQ-VAS score, which ranges from 0 for worst imaginable health state to 100 for best imaginable health state. Overall scores for the EQ-5D-5L index range from -0.594 to 1, with low scores representing a higher level of dysfunction.

Patient responses on the level of severity on the 5 EQ-5D-5L dimensions will be used to derive the corresponding EQ-5D-5L utility values, as per published methodology.

8.3.3.2. Analysis of Health Outcome Assessments

Patient-reported health-related quality of life measures (EORTC QLQ-C30 and EQ-5D) will be summarized by treatment group and visit. Differences between treatment groups will be described using an F test from a random effects mixed model with treatment, time, number of prior HER2-directed regimens in the metastatic setting (binary), geographic region, hormone receptor status, disease category, and the treatment by time interaction.

Endpoints that could be affected by missing values (e.g., health outcomes assessments) will be analyzed using a sensitivity analysis, including pattern mixture models. Results will be summarized by treatment group and visit.

